4.3 Study Enrollment Procedures

Patient Recruitment:

Initial recruitment efforts will start with the UC Davis Gastroenterology Clinic, and in particular, the motility disorders group. We will review scheduled patient visits and results from pH studies performed at the Midtown GI Clinic in EPIC. Patients identified as having typical GERD symptoms who have not yet tried a PPI or esophageal hypersensitivity will be contacted by [name] or their UCD gastroenterologist regarding their results and this study. The research team will contact the patient about the study only if the patient expresses interest and gives permission to the gastroenterologist to be contacted by the research team. If [name] is unable to reach the patient by phone, we will send the patient a letter in the mail or a MyChart message to inform them of the study.

Clinicians will also have copies of flyers they can hand to patients and the study research coordinator may also meet with some patients directly in the clinic. Study flyers may also be posted within the clinic. We may also recruit from primary care clinics. If a patient is interested in learning more about the study, they may request additional information during their appointment or may call the phone number on the flyer. Providers may also obtain verbal permission to give their prospective subjects' contact information to a study staff member who can provide further details about the study. This information may be shared with study staff in the form of an Epic patient list. We will also recruit using Study Pages and may use similar electronic recruiting platforms.

We will also recruit patients from the UCD Otolaryngology Reflux Clinic using procedures similar to those described above.

Patient Screening:

Potential subjects will undergo a telephone or in person prescreen by study staff and have the opportunity to ask questions about the study (see telephone script). Potential subjects will be informed that the study involves taking amitriptyline or omeprazole (depending upon their diagnosis and treatment plan with their physician) daily for 8 weeks. Assuming the potential subject receives care at UC Davis, their medical record will be reviewed as part of the eligibility assessment. A standardized form (see attached) will be used to ascertain potential eligibility and an electronic screening log will be kept to keep track of reasons for ineligibility. Those who are deemed potentially eligible and are interested in participating will be sent a 7 day baseline symptom diary (by email or via the post office) and scheduled for a baseline visit and 8 week follow-up visit. Potential subjects will be mailed a copy of their medication list and asked to update it or bring a complete list of medications, vitamins, herbs, and supplements that they are taking to the baseline visit. Potential subjects will be called several days after the diary is mailed to ensure that they received it and that the instructions for completing the diary are clear. One day prior to the scheduled study visit, potential subjects will also be called and screened for COVID-19 symptoms/exposure to ensure the safety of the study staff and other employees of UD Davis Health.

Baseline Visit and Consent:

At the first study visit, the baseline symptom diary will be reviewed by a study team physician (one of the study investigators) and potential subjects will be rescreened. If

they are deemed eligible, they will have an opportunity to review the written informed consent document, ask any questions, and will be consented by a study team physician. The consent process will include a discussion of the risks and benefits of taking amitriptyline or omeprazole (whichever medication is most appropriate to their condition).

To avoid alerting subjects to the fact that we are directly studying the effect of the patient-provider relationship on health outcomes (which could influence study results^{69,70}), subjects will be told during the consent process that 1) we are studying the relationship between their symptoms, their physiology, and their response to amitriptyline or omeprazole and 2) we are studying whether physicians mirror patients' physiology as has been suggested by some neuroimaging studies^{40,71} (to explain why providers are being similarly monitored). While it is challenging to study patient-provider interactions without subjects' direct knowledge, particularly since both are being monitored in this study, we believe that framing the study in this way is the most sensible way to proceed and the least likely to substantively affect the study's results. As the standard vs. expanded visit intervention is minimal risk, we believe it meets the federal criteria for modification of informed consent⁷², which allows us to conceal from participants that we are studying the patient-provider interaction.

Individuals who sign the informed consent document and elect to participate in the study will be considered enrolled. Only individuals who can provide informed consent will be eligible to participate.

Provider Recruitment and Screening:

We will advertise the study to primary care internal medicine and family medicine physicians and nurse practitioners via email. We may also recruit providers from the division of gastroenterology. We may also present the study at practice group meetings. Providers must be willing to adhere to the study protocol and not provide specific treatment recommendations (pharmacologic or non-pharmacologic) as this is outside the scope of the study. Providers must also be willing to receive a brief training to understand how to deliver the standard and expanded visit interventions.

Provider Consent:

Participating providers will be consented by the study PI. As study providers will deliver both visit interventions, they will be trained in both visit type formats. Providers will be notified of which intervention they are delivering immediately before walking into the room to conduct the study visit.

Randomization:

Once enrolled, subjects will be randomized to receive either the standard visit intervention (n=30) or the expanded visit intervention (n=30). They will not know that there are two possible visit choices. This aspect will be revealed to subjects during a debriefing at the follow-up visit at the end of their participation in the study. We will stratify by provider and create permuted block sizes of 2 and 4 with the intent to enroll 5-6 providers who will each see 10-12 subjects. If a provider cannot commit to this many

visits, the study biostatistician may need to adjust the randomization scheme and we will consent additional providers.

5. STUDY INTERVENTIONS

5.1 Interventions, Administration, and Duration

Subjects will be randomized to receive either a “standard visit” or an “expanded visit” with a study provider. The standard visit is based on a high quality, empathic, conventional primary care encounter. The expanded visit is based on an integrative medicine consultation. Both visits are based on a script of questions and statements to the patient/subject (see Appendix E). The standard visit script includes questions about GERD history, symptoms, prior evaluation and treatments, and past medical history as well as a brief physical exam. The expanded visit script includes the same questions as the standard visit script plus additional questions that inquire about the modalities of their GI symptoms (e.g., nature of the reflux taste, sensation of heartburn pain and/or abdominal fullness, time of day better/worse), details about non-GI symptoms, quality of sleep, the effect of the weather on symptoms, food cravings and aversions, menstrual flow, fears/phobias, and overall temperament. In this way, the expanded visit tries to understand the patient’s/subject’s constitution in a way that many systems of integrative medicine attempt to do. To reduce the potential for introducing bias by using the words “standard” and “expanded”, the visit templates that the study providers will follow will simply refer to the number of questions to be asked on the template (e.g., 6 Question Template).

At the end of both the standard and expanded visits, the provider will recommend the subject take the study medication and describe how to take it and what to expect. Subjects will receive the same scripted advice in both groups. Each subject will receive an 8-week supply of amitriptyline or omeprazole with instructions for how to take it (10 mg daily at bedtime or 20 mg daily when waking up, respectively).

In our pilot study⁶⁴ we did not limit the amount of time spent with the study subject. On average, the standard visit lasted 18 minutes (range 11-32 minutes) and the expanded visit lasted 42 minutes (range 23-74 minutes). The study providers will be instructed to maintain equal empathy in both groups (e.g., kind and friendly manner, maintain eye contact, active listening and repeating back the patient’s words, expressions of empathy). Thus, the main differences between the visits will be the length of time spent with the subject and the additional questions that are asked.

Each study provider will participate in an orientation session to learn how to deliver the standard and expanded visit interventions. Providers will be explicitly instructed not to offer lifestyle treatment advice for GERD to maintain uniformity of the intervention across providers. The study PI will review video recordings of the interactions to offer feedback to study providers and ensure protocol fidelity. As each study provider finishes his/her portion of the study, the PI will interview them to understand their experiences of the study, the two visit types, and their views on the doctor-patient relationship.

5.2 Handling of Study Interventions

To minimize potential bias that could affect study staff interactions with subjects, the subject will be randomized immediately before the study visit and the study provider will receive the appropriate study visit script. At the time of consent, study subjects will not be informed about the two different interview types or that part of the study involves testing the effect of the doctor-patient interaction on response to treatment. Concealment of these aspects of the study protocol is essential to maintaining the validity of the study as data suggests that patients' responses change when they know that the doctor-patient interaction is being studied^{69,70}. The study PI, or another study team member, will notify subjects at their follow-up study visit, after the exit interview, that there were two possible types of physician visits, that this aspect of the study was concealed from them initially, and of the rationale for doing so. A script outlining this planned debriefing is present in Appendix F. We believe that this intervention is minimal risk and that our plan meets the federal criteria for permitting alteration of some elements of informed consent⁷².

Subjects will be informed about taking amitriptyline or omeprazole as part of the study during the consent process and the study physician will discuss this with them during the study visit. Subjects will receive a container with an 8 week supply of the medication from a study team member at the end of the study visit.

5.3 Concomitant Interventions

5.3.1 Allowed Interventions

Subjects are permitted to remain on all baseline medications, over-the-counter products, and dietary supplements, including those used to treat GERD symptoms during the study. We will request that they not change doses of medications used to treat GERD symptoms during the 8 weeks that they are enrolled in the study.

5.3.2 Required Interventions

Amitriptyline 10 mg or omeprazole 20 mg daily for 8 weeks.

5.3.3 Prohibited Interventions

We will ask subjects not to increase their dose of GERD medications, add additional GERD medications, or change their GERD treatment regimen (with the exception of introducing amitriptyline or omeprazole) during the study. This will be monitored via the daily symptom diary and a follow-up visit medication review.

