4.2 Exclusion Criteria

Any candidates eligible to receive an 8-week supply of amitriptyline meeting any of the following exclusion criteria at baseline will be excluded from study participation.

- Diagnosis of Crohn's disease, systemic sclerosis, known active ulcer disease, gastric cancer, or untreated/active Barrett's esophagitis based on subject self-report and/or medical record review (rationale: heartburn symptoms may be due to another, more serious medical illness)

- Heavy alcohol use (> 6 drinks/week for women and > 13 drinks/week for men) based on subject self-report (rationale: can exacerbate heartburn symptoms)
- Pregnant, attempting to become pregnant, or breast-feeding (rationale: feasibility/medical safety - amitriptyline is not recommended in pregnancy or breast-feeding and the physiology of heartburn is different in pregnant women).
- Dementia or significant memory difficulties as determined by the study team and medical record review (rationale: feasibility and human subjects concerns)
- Severe, unstable psychiatric disease based on subject self-report, study team determination, and/or medical record review (rationale: feasibility and human subjects concerns)
- Bipolar disorder, concurrent treatment with a SSRI or another antidepressant that interacts with tricyclic antidepressants (rationale: medical safety)
- Prolonged QTc or severe heart disease (rationale: medical safety – amitriptyline can prolong cardiac conduction).
- History of seizure disorder (rationale: medical safety – amitriptyline can lower the seizure threshold).
- Severe liver impairment – e.g., cirrhosis, hepatocellular carcinoma, hepatitis (rationale: medical safety, not recommended in patients with hepatic impairment).
- Currently taking a tricyclic antidepressant, allergy to tricyclic antidepressants, or another medical contraindication to taking amitriptyline or related medications (rationale: safety and feasibility).
- Greater than 15 doses of nonsteroidal anti-inflammatory drugs (NSAIDS) within the prior 30 days (aspirin \leq 325 mg daily permitted) or ongoing NSAID use at a level deemed likely to interfere with the study (rationale: NSAIDS can exacerbate GERD and cause peptic ulcers)
- Failure to complete the baseline symptom diary for at least 6 of 7 days (rationale: feasibility)

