- Amitriptyline: The most common side effects are dry mouth, sleepiness, and constipation. Less common side effects include dizziness, fatigue, headache, agitation, tremor, blurred vision, nausea, insomnia, and sexual dysfunction. Rare side effects include an allergic reaction, changes in heart conduction causing slowing or speeding up of the heart rate, serotonin syndrome, and suicidal ideation. We are prescribing low doses of this medication and have excluded those most vulnerable to adverse effects and so do not anticipate any serious adverse events. If a study subject calls with concerns about side effects, they will be directed to speak with a physician on the study team to assess their symptoms and determine whether any dose modification or further evaluation is needed. If it is deemed that the subject should stop the medication, they will be instructed in how to do so. If it is determined that they need further medical evaluation, they will be instructed what to do.
- Omeprazole: The most common side effects are headaches, abdominal pain, diarrhea, and nausea. Less common side effects include skin rash, constipation, dizziness, and back pain. Rarely someone may develop a hypersensitivity reaction, acute interstitial nephritis, lupus, or an enteric infection. Long-term use may increase the risk of

fractures, vitamin B12 deficiency, or low magnesium levels. Despite these risks, omeprazole is generally well-tolerated and available over-the-counter. If a study subject calls with concerns about side effects, they will be directed to speak with a physician on the study team to assess their symptoms and determine whether any dose modification or further evaluation is needed. If it is deemed that the subject should stop the medication, they will be instructed in how to do so. If it is determined that they need further medical evaluation, they will be instructed what to do.

- Severe GERD symptoms: It is possible that subjects may experience a flare in their GERD symptoms during the study. If a subject calls with severe GERD symptoms, he or she will be directed to speak with a study physician to discuss their symptoms and determine the best course of action. In some cases as needed antacids may be recommended for refractory symptoms. If this recommendation does not suffice, the subject may need to initiate additional medication and possibly be removed from the study.

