7.1 Specification of Safety Parameters

As amitriptyline is known to cause cardiac conduction delays and lower the seizure threshold in some individuals, we will not enroll anyone with known cardiac disease or seizure history that would be allocated amitriptyline during the study. We will also not enroll anyone with bipolar disorder (to avoid causing mania) or medications that could interact with amitriptyline and cause serotonin syndrome that would be allocated amitriptyline during the study.

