7.2 Methods and Timing for Assessing, Recording, and Analyzing Safety Parameters

Subjects will be instructed to call the research team if they have any questions or concerns during the study period. A research team member will call subjects approximately 1 week into the study period to confirm that they are taking their study medication as prescribed and to see if they have any questions or concerns. If so, a physician on the study team will reach out to them.

When subjects return for their follow-up visit, a study team member will inquire about any changes to their health or medical visits (including emergency room visits or hospitalizations) since their initial study visit. We will ask specifically if they experienced any adverse effects from the amitriptyline or omeprazole. If a subject reports a new or worsening symptom that is medically concerning (e.g., bright red blood per rectum), they will be referred for further evaluation.

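### In the visible text, the bar on drugs that interact with amitriptyline applies only at enrollment; during the 8 weeks the protocol restricts GERD treatment alone.

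*Combined protocol and SAP*

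**What the plan says.** All places are in the combined protocol and SAP.

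- **Entry.** Section 4.2 states that amitriptyline candidates "meeting any of the following exclusion criteria at baseline will be excluded from study participation". One criterion is "concurrent treatment with a SSRI or another antidepressant that interacts with tricyclic antidepressants (rationale: medical safety"). Section 7.1 says the trial will not enroll people on "medications that could interact with amitriptyline and cause serotonin syndrome" if they would be given amitriptyline.
- **On treatment.** Section 5.3.1 lets subjects stay on all baseline medicines and asks that GERD doses stay fixed. Section 5.3.3, on prohibited interventions, reads "We will ask subjects not to increase their dose of GERD medications, add additional GERD medications, or change their GERD treatment regimen", apart from introducing the study drug itself. Compliance is checked through the symptom diary and the medication review at follow-up.
- **Expected harm.** Section 7 lists serotonin syndrome among the rare side effects of amitriptyline. It says that doses are low and that the investigators "have excluded those most vulnerable to adverse effects and so do not anticipate any serious adverse events".
- **Safeguards.** Section 7.2: "Subjects will be instructed to call the research team if they have any questions or concerns during the study period". Section 7: "If a study subject calls with concerns about side effects, they will be directed to speak with a physician on the study team". Under section 8 a study physician may stop the drug, and the subject is then still followed to 8 weeks.

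**The concern.** Having no interacting drug at Day 0 does not prevent one from being started later. A subject can enter without an antidepressant and be prescribed one by another clinician a few weeks afterwards. The protocol treats that combination as unacceptable at entry on grounds of medical safety, and rests part of its expectation of no serious adverse events on having excluded vulnerable people. The drug-interaction part of that reasoning holds through week 8 only if the restriction also runs through week 8. The visible on-treatment rules do not carry it forward.

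What is at stake is the safety of individual amitriptyline subjects. Serotonin syndrome is the only harm that the documents link to interacting drugs.

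**Working it through.** The documents give no figure to reproduce here. The check sets the entry rule beside the on-treatment rules, and then asks which scheduled contact would reveal a newly started drug.

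**Step 1: rules compared.** The entry rule covers SSRIs, other interacting antidepressants and drugs that could cause serotonin syndrome (4.2, 7.1). The on-treatment rule covers changes to GERD treatment (5.3.1, 5.3.3). They overlap in one case. Section 2.1 names serotonin reuptake inhibitors among the agents used for functional heartburn, so an SSRI added for heartburn is an added GERD medication and 5.3.3 already forbids it. The uncovered case is an interacting drug started for another indication.

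**Step 2: scheduled contacts.**
- Medication list (6.1): taken at Visit 1 and Visit 2 only.
- Symptom diary (6.2.3, 6.27): records products used to manage symptoms. The Précis places the on-study diary in weeks 1 and 8, so it does not cover weeks 2 to 7.
- Check-in calls (6.2.6): diary reminder, medication reminder, subject's questions or concerns, appointment. Section 7.2 describes the one-week call as being "to confirm that they are taking their study medication as prescribed and to see if they have any questions or concerns". Neither section lists a question on new medicines.
- Health concerns raised in those calls (7.3): recorded, but not actively asked for.

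None of these asks about a new non-GERD medicine before Visit 2.

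**Step 3: timing.** Inputs: Visit 2 on Day 53-60 (6.1), first call about one week after Visit 1 and second call one week before Visit 2 (6.2.6), and an 8-week supply (5.1). Assume that dosing starts at about Day 0 and no doses are missed.
- Supply: 8 × 7 = 56 days.
- Visit 2 relative to the end of supply: 56 − 53 = 3 days before, to 60 − 56 = 4 days after. The medication review comes when treatment is essentially over.
- Second call: 53 − 7 = Day 46, to 60 − 7 = Day 53.
- Interval between the calls: 46 − 7 = 39 days, to 53 − 7 = 46 days.
- Supply left at the second call: 56 − 53 = 3 days, to 56 − 46 = 10 days.

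A question at the calls would therefore catch a drug started in week 1 early. For a drug started after the first call, it brings discovery forward by only the 7 days between the second call and Visit 2. The rule in 5.3.3 has to do most of the work, because it acts before the drug is started. These figures describe the schedule and do not measure risk.

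**The case against.** The strongest objection is that the warning may exist where this review cannot see it. Subjects discuss the risks of amitriptyline with a physician at consent (4.3, 6.2.3) and receive scripted advice on taking it (5.1). The consent form, the visit scripts (Appendix E) and the safety monitoring plan (Appendix G) were not available. A reader might infer that subjects go unwarned, and the documents do not support that. What stands is narrower: 5.3.3 and the listed content of the calls do not state the restriction.

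It is also fair to say that exclusion criteria normally apply at baseline, that section 5.3 reads mainly as protection of the symptom outcome, and that the risk is small. The dose is 10 mg daily. Bipolar disorder and severe, unstable psychiatric disease are excluded, which plausibly removes some of the people likeliest to start an antidepressant. Section 9.4 convenes the safety monitor after a serious adverse event likely due to the drug, and 7.3 sets expedited reporting for unexpected, related serious events. All of this stands and keeps the point minor. But the safeguards in sections 7, 7.2, 8 and 9.4 respond once someone has a concern or an event has occurred.

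Other stronger readings also lack support. Section 7.1 ties conduction effects to known cardiac disease, with no mention of interacting drugs. The omeprazole list in 4.2 is also worded as current use, but the documents describe no particular harm from those combinations. Nothing suggests an effect on the comparison of visit types.

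Finally, a lay subject may not recognise an interacting drug. That objection is sound, and the fix is worded with it in mind.

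**Conclusion.** The point holds in a limited form, as a low-cost safety improvement. In the visible text, the plan permits during treatment a drug combination that it bars at entry for medical safety, provided the drug is started for a non-GERD reason, and no scheduled question would reveal it before Day 53-60. The number of subjects affected cannot be estimated, because the documents give neither a rate of new prescriptions nor the split between amitriptyline and omeprazole. The conclusion assumes that the unseen consent form and appendices do not already state the restriction. If one of them does, all that remains is a missing cross-reference in 5.3.3 and, optionally, the call question. Sample size and analysis need no change.

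**What to change.** Add to 5.3.3: *Subjects taking amitriptyline will be asked not to start an SSRI, another antidepressant, or any other drug that could cause serotonin syndrome with amitriptyline during the 8 weeks without first contacting the study team, and to tell any prescriber that they are taking amitriptyline.*

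Naming antidepressants as a class, and asking the subject to tell prescribers, avoids relying on a lay person to judge interactions. Naming the drugs is also safer than pointing to everything barred in 4.2, which would pull in the NSAID limit, set there for a different reason.

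As a back-up, add one question on newly started medicines to each of the two check-in calls in 6.2.6. Positive answers go to a study physician, who decides under section 8 whether to stop amitriptyline, with follow-up continuing to 8 weeks.

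The cost is one sentence, one scripted question per call, and possibly a few more discontinuations of study drug. If the consent form, Appendix E or Appendix G already gives the warning, cite it in 5.3.3 in place of the new sentence.
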